### **6.11.2 Clinical Laboratory Evaluation**

Observed values and change from baseline in haematology, biochemistry and urinalysis assessments will be summarised over time. If the test results are reported in categorical format, the results will be summarised by subject counts and percentage for each category.

Each haematology, biochemistry and urinalysis parameter will be classed as low, normal, high, missing based on the reference ranges. Shift tables in relation to the normal range from baseline over time will be presented.

Haematology, biochemistry and urinalysis data will be listed separately including change from baseline, reference ranges flagging all out of range values and their clinical significance.

Listings of clinically significant haematology and biochemistry laboratory measurements recorded throughout the study will be provided.

### **6.11.3 Viral Serology**

Viral serology values will be listed.

### **6.11.4 Vital Signs**

Vital sign observed values and change from baseline by parameter (unit) will be summarised over time.

All vital sign data will be listed including change from baseline.

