## 6 ANALYSIS PLAN

### 6.1 General

Summary statistics for continuous variables will consist of number of non-missing observations (n), mean, SD, minimum, median and maximum, unless specified otherwise.

For categorical variables the number and percentage of subjects in each category will be presented, based on the number of non-missing observations apart from disposition of subjects, protocol deviations, background and demographic characteristics, prior and concomitant medications/procedures and AEs where the percentage will be based on the number of subjects in the analysis set with a missing category presented where applicable.

The mean and median will be displayed to 1 more decimal place than the original data values and the SD will be displayed to 2 more decimal places than the original data values. The minimum and maximum will be displayed to the same number of decimal places as the original data. Percentages will be displayed to 1 decimal place; except percentages will not be presented when the count is zero and 100% for count data will be presented as an integer.

All statistical tests will be performed using a two-tailed 10% overall significance level, unless otherwise stated. The null hypothesis at all times will be that the treatments are equivalent. All comparisons between the treatments will be reported with 90% confidence intervals (CIs) for the difference.

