### 6.4 Data Presentations

The data will be summarised in tabular form by treatment group apart from disposition of subjects, prior and concomitant medications and background and demographic data which will be summarised by treatment group and overall subjects.

Treatment groups will be presented in the following order using these labels:

- SoC + C21 100 mg b.i.d
- SoC + Placebo

Listings will be sorted by treatment group, site and subject number and date/time of assessment.

Data will be summarised and listed using the following analysis sets:

	Enrolled	RAS	FAS	PPAS	SAS
Tables	
 
• Disposition
 
	
 
• Withdrawal
 
	
 
• Demography
 
• Efficacy
 
	
 
• Demography
 
• Efficacy (primary endpoint only)
 
	
 
• Demography
 
• Prior and concomitant medications
 
• Medical history
 
• Exposure
 
• Safety
 

Listings	
 
• Completion/ withdrawal
 
• Eligibility
 
	
 
• Protocol deviations
 
• Analysis sets
 
• Demography
 
• Medical history
 
• Disease under investigation
 
• Hospitalisation
 
• Visit dates
 
• Randomisation
 
• Efficacy
 
• Biomarkers
 
			
 
• Prior and concomitant medications
 
• Safety
 
• IMP administration
 
• Exposure
 

1. Demography will be summarised using the FAS and repeated for the PPAS and SAS where the analysis sets differ for at least 1 subject. If either of these analysis sets are identical to the FAS the summary will not be presented.

Only scheduled post baseline data will be tabulated, post-baseline repeat/unscheduled assessments will not be included in tables, although they will be listed and in particular all clinically significant values will be noted.

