The most frequently reported treatment-emergent adverse events (TEAE) related to C21 treatment was headache. Other TEAEs related to C21 treatment included dizziness, nausea, and fatigue that were reported by 2 subjects and pruritus, rash, vomiting, and diarrhoea that were reported as single events. One incidence of syncope of moderate intensity was reported as being related to C21 treatment (100 mg C21; C21-002-16) and one incidence of presyncope was observed and assessed as related to C21 treatment (100 mg C21; C21-002-16).

One episode of clinically significant PR prolongation was reported in 1 subject's ECG, recorded 1 hour after intake of 3 mg C21 (C21-001-16). This event was assessed as related to C21 treatment. However, a causal relationship with C21 treatment could not be confirmed or excluded and at this stage, it cannot be excluded that C21 could cause slowing of atrioventricular conduction (= PR prolongation) in susceptible individuals, although it is considered unlikely with a documented first and second degree atrioventricular block in the subject 1 month after the treatment period and given the reassuring telemetry findings within the recent phase 1 trial (C21-003) that C21 treatment did not affect ECG values.

There were no clinically significant abnormal findings in the safety laboratory parameters that were considered to be related to C21 treatment and no clinically significant findings or dose-related trends in blood pressure, heart rate, and ECG except for the above mentioned PR prolongation.

No serious adverse events (SAEs) or deaths observed during the 3 phase 1 trials.

In addition, a phase 2a trial in subjects with Raynaud's phenomenon secondary to SSc (SSc-RP) to show proof of mechanism of C21 on vasodilation is currently ongoing.

For further details, please refer to the current Investigator's Brochure.

Vicore Pharma AB
Version: 2.0
Trial ID: VP-C21-006
Date: 14-Aug-2020

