5.4.1 Withdrawal from Trial IMP

If a subject is prematurely withdrawn from IMP, the Investigator must make every effort to perform the withdrawal assessments described in Section 6.5.3, and further perform end-of-trial Visit (Visit 9) 7-10 days after the last dose of IMP.

A subject will be withdrawn from IMP if any of the following occurs:

- Need for mechanical invasive or non-invasive ventilation
- Discharge from the hospital/controlled facility
- Major protocol deviations as defined by Sponsor.

Vicore Pharma AB Version: 2.0 Trial ID: VP-C21-006 Date: 14-Aug-2020

• Sponsor decision to stop the trial or to stop the subject's participation in the trial; reasons may include medical, safety, or regulatory issues, or other reasons consistent with applicable laws, regulations, and GCP.

- It is the wish of the subject for any reason
- The Investigator judges it necessary due to medical reasons
- Adverse events such as:
 - Serious cardiovascular complications such as severe peripheral oedema or significant bradycardia indicating a potential risk for the subject as evaluated by the Investigator
 - o Moderate to severe skin rashes as judged by the Investigator e.g. Stevens-Johnson syndrome and toxic epidermal necrolysis
- Pregnancy

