8.2.6 Electrocardiogram

12-lead electrocardiography (ECG) will be recorded at Visit 1.

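### No planned vital-sign table counts the subjects per arm with a marked pulse or blood pressure value on treatment, and unscheduled extremes appear only in listings

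*SAP*

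**What the plan says.** SAP 6.11.4 is short. Its table plan reads "Vital sign observed values and change from baseline by parameter (unit) will be summarised over time", and its listing plan reads "All vital sign data will be listed including change from baseline". It names no statistics of its own, so the default in SAP 6.1 applies: "Summary statistics for continuous variables will consist of number of non-missing observations (n), mean, SD, minimum, median and maximum, unless specified otherwise".

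SAP 6.4 restricts what enters any table: "Only scheduled post baseline data will be tabulated, post-baseline repeat/unscheduled assessments will not be included in tables". The sentence continues: "although they will be listed and in particular all clinically significant values will be noted".

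On the risk itself, protocol 3.5 discusses one phase 1 case of PR prolongation and concludes that "it cannot be excluded that C21 could cause slowing of atrioventricular conduction" in susceptible individuals, while calling this unlikely. Protocol 3.4 reports raised blood pressure and conduction changes in dogs. Protocol 5.4.1 lists, among the adverse events that lead to withdrawal from IMP, "Serious cardiovascular complications such as severe peripheral oedema or significant bradycardia".

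Protocol 8.2.6 states "12-lead electrocardiography (ECG) will be recorded at Visit 1"; no later ECG is scheduled, and SAP 6.11.5 only lists the screening interpretation.

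**The concern.** A drug effect on conduction would be expected to show as a strong effect in a few subjects, not as a small shift in everyone. A summary by visit suits the second pattern and serves the first poorly. The natural safety question is how many subjects in each arm had a marked pulse or pressure value at any time on treatment, and no planned vital-sign table answers it.

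The scheduled-only rule adds to this. A repeat or unscheduled reading is often taken because something looked wrong, and those are the readings that the tables leave out. The withdrawal assessments (protocol 6.5.3 and the withdrawal column of Table 1) contain no vital signs. A reading between visits that leads to stopping IMP would therefore be unscheduled and stay out of the tables, and the subject would then leave the later visit summaries.

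Safety profile is a stated secondary objective, this is the first trial of C21 in COVID-19 (protocol 3.6), and no data monitoring committee is planned (protocol 14). A reader of the report will rely mainly on the tables.

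**Working it through.** The plan gives no figure on this point, so there is none to reproduce. The check has two parts: what each planned output can show, and an illustration of size.

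**What each output shows**

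- Vital-sign tables by visit (SAP 6.11.4 with 6.1): n, mean, SD, minimum, median and maximum of value and change. They show one extreme scheduled value per arm and visit. They do not show how many subjects are affected, or whether low minima at several visits come from one subject or several.
- Vital-sign listing: every reading, including unscheduled ones, but no count by arm.
- Laboratory data, for comparison (SAP 6.11.2): shift tables against the normal range and out-of-range flags. SAP 6.11.4 has neither.
- Adverse event tables (SAP 6.11.1): counts of subjects by arm, including events that lead to treatment withdrawal. Protocol 8.2.7 says when a laboratory abnormality must be reported as an adverse event. There is no such rule for pulse or blood pressure, so capture depends on the investigator's judgement.

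**Size of the effect on a visit mean**

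From the documents: 75 subjects per arm. Assumed, because the documents give no figures: a drop of 40 bpm in three subjects, and an SD of change of 10 to 15 bpm.

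- Three subjects at the same visit: 3 × 40 / 75 = 1.6 bpm.
- One subject at a given visit: 40 / 75 = 0.53 bpm.
- Standard error of the difference between arms: SD × √(2/75) = 1.63 bpm at SD 10 and 2.45 bpm at SD 15.
- Drops seen only at unscheduled readings: 0 bpm in every table.

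**Effect on the other statistics**

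Pulse was simulated for 75 subjects at one visit (assumed mean 80 bpm, normal, 4,000 repeats), with one or four subjects set to 40 bpm.

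| Assumed SD | Mean shift, 1 / 4 subjects | SE of arm mean | Median shift, 1 / 4 | Minimum, none affected | Minimum, 1 / 4 |
|---|---|---|---|---|---|
| 10 | −0.53 / −2.14 | 1.15 | −0.17 / −0.70 | about 56 | 40.0 / 40.0 |
| 12 | −0.54 / −2.14 | 1.39 | −0.20 / −0.83 | about 51 | 39.9 / 39.9 |
| 15 | −0.54 / −2.13 | 1.73 | −0.25 / −1.05 | about 44 | 38.8 / 38.9 |

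With four subjects affected, the mean shift is 2.14 / 1.63 = 1.3 standard errors of the arm difference at SD 10, and 2.13 / 2.45 = 0.9 at SD 15. The minimum does react, clearly at SD 10 or 12 and weakly at SD 15. It does not distinguish one affected subject from four.

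**How complete the scheduled readings are**

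Protocol Table 1 and section 8.2.5 place vital signs at every visit up to Visit 8. The Visits 3-8 list in section 6.5.2 attaches them to the short physical examination in words that can be read as leaving them to the investigator's judgement. The two readings give different denominators for the tables by visit.

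**The case against.** A reader might infer that marked bradycardia in a few subjects would leave no trace in the tables, or that pulse and blood pressure are the only on-treatment data on this risk. The documents support neither.

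- Minimum and maximum are tabulated for value and for change, so an extreme scheduled reading is visible.
- Adverse events are collected from consent to Visit 9, every event that meets the definition has to be reported (protocol 9.3), and short physical examinations run at Visits 2-8. Abnormal on-treatment findings enter the adverse event data (SAP 6.11.6).
- A subject who stops IMP because of an adverse event of bradycardia is counted by arm among TEAEs leading to treatment withdrawal. Leaving later visit summaries does not remove that subject from view.
- Nothing is lost, because every reading is listed and SAP 6.4 says that clinically significant values will be noted.
- The prior evidence is mild. Protocol 3.5 calls a causal effect on conduction unlikely, cites reassuring telemetry, and reports no dose-related trend in heart rate or blood pressure. Pulse is also only an indirect measure of a PR effect.
- The SAP follows the descriptive plan in protocol 13.4.2, and the table shells are in a separate document that was not available here.

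All of this stands and limits the point. It does not supply the missing count. The minimum is one value per visit, adverse event capture rests on judgement without a stated criterion for vital signs, and a listing is not a comparison between arms.

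**Conclusion.** The point holds in a narrow form. The vital-sign tables give no count per arm of subjects with a marked pulse or blood pressure value on treatment, they cannot show whether extremes at different visits belong to one subject or several, and unscheduled extremes appear only in listings. This is a gap in safety reporting that is cheap to close. It does not hide data, and it does not affect the primary analysis.

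The absence of the count follows from the text of SAP 6.1, 6.4 and 6.11.4 and needs no assumption, unless the unseen shells already add such a table. The sizes in bpm rest on assumed values (mean 80, SD 10 to 15, affected subjects at 40 bpm or dropping by 40 bpm). They illustrate the pattern and do not predict this trial's data.

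**What to change.** In SAP 6.11.4, on the SAS by actual treatment, add:

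1. Each subject's worst on-treatment value and worst change from baseline, for lowest pulse and for highest and lowest systolic and diastolic pressure. Include repeat and unscheduled readings, and state the on-treatment window.
2. The number and percentage of subjects per arm in bands of that worst value, with cut-points set by the sponsor before unblinding.
3. The number of readings per subject, by arm, alongside.

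In SAP 6.4, exempt this table from the scheduled-only rule. The laboratory shift tables need no change on this account.

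The sponsor should also reconcile protocol 6.5.2 (Visits 3-8) with Table 1 and section 8.2.5, so that it is clear whether vital signs are required at each of these visits.

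The cost is a few lines of SAP text and one or two tables from data already collected. The drawback is that subjects with more unscheduled readings have more chances of an extreme value; item 3 lets the reader judge whether the arms differ in this respect.

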### **6.11.5 Electrocardiography**

Details of the electrocardiogram (ECG) interpretation at Screening will be listed.

### **6.11.6 Physical Examination**

Abnormal physical examination findings will be included within medical history if identified prior to first administration of study treatment, or within adverse events if identified after first administration of study treatment. They will not be summarised independently. Details of timings of physical examinations will be listed.

**6.11.7 Pregnancy Test**

Pregnancy test details, including the date and method of sampling, will be listed.

**6.11.8 Visit Dates**

Dates of each visit for each subject will be listed.

**6.12 Changes from the Protocol Planned Analysis**

- The SAS definition has been amended to clarify that subjects do not need to be randomised to be included. A subject will be included if they have received study treatment, irrespective of their randomisation.
- The secondary endpoint of time on oxygen supply has been amended to include all subjects and not just those who do not require invasive or non-invasive mechanical ventilation.
- Abnormal physical examinations will not be summarised. This data forms part of medical history or adverse events and will be summarised within these data.

All dates expressed in MM/DD/YYYY (US)

**Document name:** VP-C21-006 OCH20005 SAP Final 1.0  
**Document created:** 09/10/2020 13:21:34  
**Document pages:** 20  
**Document ID:** 9c06cb3f2cd942b3b52c7629656ed9f207054180  

1 PROTOCOL SUMMARY

Trial Title	A randomised, double-blind, placebo-controlled, phase 2 trial investigating the safety and
	efficacy of C21 in hospitalised subjects with COVID-19 infection not requiring mechanical
	ventilation
Trial ID	VP-C21-006
Trial p	2
Objectives	Primary objective
	To investigate the efficacy of C21 200 mg daily dose (100 mg b.i.d.) on COVID-19 infection not requiring mechanical invasive or non-invasive ventilation
	Secondary objectives
	To evaluate the following of C21 200 mg daily dose (100 mg b.i.d.)
	• Effect on inflammation
	Safety profile
	Exploratory objectives
	To investigate a range of laboratory parameters as potential biomarkers of inflammation and
	viral load, following oral administration of C21 200 mg daily dose (100 mg b.i.d.).
Endpoints	Primary endpoint
-	• Change from baseline in C-reactive protein (CRP) after treatment with C21 200 mg daily dose (100 mg b.i.d.)
	Secondary endpoints
	1) Change from baseline in:
	Body temperature
	• IL-6
	• IL-10
	• TNF
	• CA125
	• Ferritin
	2) Number of subjects not in need of oxygen supply
	3) Number of subjects not in need of mechanical invasive or non-invasive ventilation
	4) Time to need of mechanical invasive or non-invasive ventilation
	5) Time on oxygen supply (for those not needing mechanical invasive or non-invasive
	ventilation 6) Adverse events
	6) Adverse events
	Exploratory endpoints
	Blood samples will be saved for potential future analyses of biomarkers reflecting
	inflammation and lung injury

Vicore Pharma AB Version: 2.0 Trial ID: VP-C21-006 Date: 14-Aug-2020

T . ID .									
Trial Design	A randomised, double-blind, placebo-controlled trial evaluating the efficacy and safety of C21 200 mg daily dose (100 mg b.i.d) on top of standard of care for 7 days.								
	Approximately 150 subjects with COVID-19 infection will be randomised 1:1 to receive								
	either standard of care + C21 (N=75) or standard of care + placebo (N=75).								
	All subjects will be followed-up 7-10 days after receiving the last investigational medicinal								
	product (IMP) dose (visit or phone call, if recovering at home)								
Inclusion	1) Written informed consent, consistent with ICH GCP R2 and local laws, obtained before								
Criteria	the initiation of any trial related procedure								
	2) Diagnosis of coronavirus (SARS-CoV)-2 infection confirmed by polymerase chain								
	2) Diagnosis of coronavirus (SARS-CoV)-2 infection confirmed by polymerase chain reaction (PCR) test \leq 4 days before Visit 1 with signs of an acute respiratory infection								
	3) Age ≥ 18 and ≤ 70 years								
	4) $CRP \ge 50 \text{ and } \le 150 \text{ mg/l}$								
	5) Admitted to a hospital or controlled facility (home quarantine is not sufficient)								
	6) In the opinion of the Investigator, the subject will be able to comply with the								
	requirements of the protocol								
Exclusion Criteria	Any previous experimental treatment for COVID-19								
Exclusion Criteria	2) Need for mechanical invasive or non-invasive ventilation								
	3) Concurrent respiratory disease such as chronic obstructive pulmonary disease,								
	idiopathic pulmonary disease (IPF) and/or intermittent, persistent or more severe								
	asthma requiring daily therapy or any subjects that have had an asthma flare								
	requiring corticosteroids in the 4 weeks (28 days) prior to COVID-19 diagnosis								
	4) Participation in any other interventional trial within 3 months prior to Visit 1								
	5) Any of the following findings at Visit 1: o Positive results for hepatitis B surface antigen (HBsAg), hepatitis C virus								
	antibody (HCVAb) or human immunodeficiency virus 1+2 antigen/antibody (HIV 1+2 Ag/Ab)								
	o Positive pregnancy test (see Section 8.2.3)								
	6) Clinically significant abnormal laboratory value at Visit 1 indicating a potential risk for the subject if enrolled in the trial as evaluated by the investigator								
	7) Concurrent serious medical condition with special attention to cardiac or ophthalmic								
	conditions (e.g. contraindications to cataract surgery), which in the opinion of the Investigator makes the subject inappropriate for this trial								
	8) Malignancy within the past 3 years with the exception of in situ removal of basal cell								
	carcinoma and cervical intraepithelial neoplasia grade I 9) Treatment with any of the medications listed below within 1 week prior to Visit 1:								
	o Strong Cytochrome p450 (CYP) 3A4 inducers (e.g. rifampicin, phenytoin,								
	St. John's Wort, phenobarbital, rifabutin, carbamazepine, anti HIV drugs, barbituates)								
	o Warfarin								
	10) Pregnant or breast-feeding female subjects								
	11) Female subjects of childbearing potential not willing to use contraceptive methods as								
	described in Section 5.3.1								
	12) Male subjects not willing to use contraceptive methods as described in Section 5.3.1								
	13) Subjects known or suspected of not being able to comply with this trial protocol (e.g. due to alcoholism, drug dependency or psychological disorder)								
	due to dicononism, drug dependency of psychological disorder)								

Vicore Pharma AB Version: 2.0 Trial ID: VP-C21-006 Date: 14-Aug-2020

A subject will be withdrawn from IMP if any of the following occurs:
Need for mechanical invasive or non-invasive ventilation
Discharge from the hospital/controlled facility
 Major protocol deviations as defined by Sponsor.
• Sponsor decision to stop the trial or to stop the subject's participation in the trial; reasons may include medical, safety, or regulatory issues, or other reasons consistent with applicable laws, regulations, and GCP.
It is the wish of the subject for any reason
The Investigator judges it necessary due to medical reasons
 Adverse events such as: Serious cardiovascular complications such as severe peripheral oedema or significant bradycardia indicating a potential risk for the subject as evaluated by the Investigator Moderate to severe skin rashes as judged by the Investigator e.g. Stevens-Johnson syndrome and toxic epidermal necrolysis
Pregnancy
Withdrawal from trial: • Enrolment in other clinical studies involving investigational products or enrolment in other types of clinical research judged not to be scientifically or medically compatible with this trial.
Disallowed treatment during the trial period
It is the wish of the subject for any reason The description of the subject for any reason of th
 The Investigator judges it necessary due to medical reasons Adverse events
 Adverse events Lost to follow-up
IMP will be delivered as 50 mg capsules packed in plastic container units with 28 capsules in each.
Each unit will contain either C21 or matching placebo.
At the trial site, IMP must be stored separately from normal clinic stocks in a securely locked area only accessible to authorised trial personnel.
Labeling of the IMP will be in local language and done in compliance with GMP Annex 13 (GMP 2003) and local regulatory requirements.
IMP will be administered twice daily to the subjects for 7 days as follows:
 Morning dose: Two 50 mg capsules (100 mg C21 or placebo) to be taken with a glass of water after minimum 2 hours fasting Afternoon/evening dose: Two 50 mg capsules (100 mg C21 or placebo) to be taken with a glass of water after minimum 2 hours fasting
Subjects will be required not to eat anything for 1 hour after taking the IMP.
Concomitant medication may be given according to local standard of care.
1 week before Visit 1 and during the trial period
 1 week before Visit 1 and during the trial period Strong CYP3A4 inducers (e.g. rifampicin, phenytoin, St. John's Wort, phenobarbital, rifabutin, carbamazepine, anti HIV drugs, barbituates) Warfarin

Confidential

Vicore Pharma AB Version: 2.0 Trial ID: VP-C21-006 Date: 14-Aug-2020

